Non-adherence to the heart failure (HF) plan of care after hospital discharge has been associated with clinical outcomes, including the combined endpoint of all-cause mortality and rehospitalization for decompensated HF. Most patients are discharged with a complex set of instructions that include multiple medications (and differing medication administration plans), sodium restricted diet, fluid management actions (daily weight monitoring and in some cases, fluid restriction), monitoring signs and symptoms of HF, activity and exercise, and when to return for follow-up. At discharge, patients (and their families) may not understand that HF is chronic. Improvement in quality of life may be dependent on patients' acceptance of HF as a chronic, irreversible condition that requires self-care monitoring and behaviors (for example, becoming or staying physically active), even when they feel fine. To decrease the complexity of understanding HF, patients receive a HF handbook and a "zones" 1-page handout before discharge. In addition, they can watch multiple video clips of many HF topics and discuss HF self-care with the hospital healthcare team. However, patients may not read (or view) education materials due to health literacy issues, cognitive decline, eyesight issues, fatigue or depression. Patients may rely on lay (family) caregivers to understand self-care expectations and be active partners in care. Caregivers engaged in patients' care may not be present at discharge or may have preconceived or inaccurate ideas about HF self-care after discharge. A recorded message that could be repeatedly played by patients and caregivers might increase adherence to post-discharge self-care behaviors and 7-day follow-up appointments, and have clinical benefits related to a reduction in all-cause mortality and rehospitalization. The purposes of this randomized, controlled study are to examine the effects of use of a novel MyROAD (Recordable On-Demand Audio Discharge) card, given to patients at discharge. The aims of this single-blind, placebo-controlled study are to examine the effects of recorded messages that can be replayed post discharge (delivered via the MyROAD card) on (1) 45-, 90-, and 180-day *first occurrence* and (2) *time to first occurrence* of all-cause and HF-related hospitalization, ED visits and death/ cardiac transplantation/ventricular assist device, (3) 45-day quality of life, symptoms, functional status and perceived adherence to activity recommendations, and (4) 7-day follow-up appointment with the healthcare provider assigned before discharge. A total of 1066 patients (968 + 10% attrition) with decompensated HF will be randomized to either usual care or usual care and receiving a MyROAD card at discharge.

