Based on historical readmission rates among subjects receiving the current standard of care treatment (~ 20% and dropping slightly every year), a 30-day readmission rate of 18% is expected. We are also basing the sample size on an expected 90-day rehospitalization rate of 25% and a 180-day rehospitalization rate of 35%; both of which are conservative. Sample size calculations were performed to show minimum sample size needed to detect a decrease of 30% at 30-days, 90-days and 180-days with the addition of the card. In many research studies, trends toward improvement are found at 30 days, but the trend is not significant till further out (90 days or 180 days). Thus, we are hypothesizing that a trend will be seen at 30 days, but that there will be significant differences at 90 days and 6-months. A total sample size of 968, 734 and 468 are needed to achieve 80% power in 30-day, 90-day and 180-day rehospitalization rates, respectively. These calculations assumed a balanced randomization and use of one-sided Pearson chi-square tests with a significance level of 0.05. Calculations were performed using SAS software (version 9.2; Cary, NC). To account for attrition in follow-up, sample size was increased by 10-% at 30-days and 20% at 90- and 180-days, creating ideal sample sizes of 1066 (533 per group; to achieve power at 30-days), 882 (441 per group; to achieve power at 90-days) and 562 (281 per group; to achieve power at 180-days).

- Thus, our *minimum sample size* will be 562 subjects. If trends in outcomes are favorable, data collection will continue to reach the required sample size for 90-day outcomes.

Analyses

Patient characteristics will be summarized using frequencies and percentages for categorical factors, and means, standard deviations, and percentiles of interest for continuous measures. Pearson chi-square tests will be used to compare the proportion of subjects meeting the composite endpoint of death or at least 1 readmission by 6 months. Secondary analyses will use Poisson regression to compare readmission rates (number of readmissions/follow-up days), and competing risk survival methods will be used to compare time to first readmission between groups. Analyses will be performed assuming a 0.05 significance level. Analyses will be performed using SAS software (version 9.2 or higher; Cary, NC).

Feasibility

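### The 30-day sample size of 968, and so the target of 1066, does not follow from the stated 18% rate; at that rate power is about 75%, not 80%

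*Combined protocol and SAP*

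**What the plan says.** The Sample Size section starts from a historical readmission rate under standard care of about "20% and dropping slightly every year" and concludes that "a 30-day readmission rate of 18% is expected". It takes control rates of 25% at 90 days and 35% at 180 days. The aim is to "detect a decrease of 30% at 30-days, 90-days and 180-days with the addition of the card". The test is a one-sided Pearson chi-square at 0.05 with equal allocation. The result is given as: "A total sample size of 968, 734 and 468 are needed to achieve 80% power in 30-day, 90-day and 180-day rehospitalization rates, respectively".

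For losses, "sample size was increased by 10-% at 30-days and 20% at 90- and 180-days", which leads to 1066, 882 and 562. The 30-day figure becomes the headline. The opening summary says "A total of 1066 patients (968 + 10% attrition) with decompensated HF will be randomized", and Sample and Setting repeats 1066 (533 per group). The Sample Size section also sets 562 as the minimum, with recruitment to continue towards the 90-day size if trends are favourable.

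**The concern.** All the inputs to the 30-day calculation are stated, so a reader should be able to reproduce 968. A lower control rate with the same relative reduction means a smaller absolute difference and a larger sample. The stated total looked too small for 18%.

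If so, the 80% power attached to the enrolment target does not follow from the plan's own assumptions. The error is also in the unfavourable direction, because the plan expects rates to fall but appears to size on the higher, older rate. Separately, adding 10% or 20% to a required number does not leave that number after a loss of 10% or 20%.

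**Working it through.** **Inputs (all from the Sample Size section).** Control rates p1 = 0.18, 0.25 and 0.35 at 30, 90 and 180 days; p2 = 0.7 × p1; one-sided alpha 0.05 (z = 1.645); power 80% (z = 0.842); equal arms; attrition 10%, 20% and 20%.

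**Formula.** Pearson chi-square for two proportions, with m = (p1 + p2)/2:

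n per group = [1.645 × √(2m(1 − m)) + 0.842 × √(p1(1 − p1) + p2(1 − p2))]² / (p1 − p2)²

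Each group is rounded up and doubled.

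**Step 1: reproduce the plan's own figures, then test the 30-day one.**

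| Rates | First term | Second term | Difference | n per group | Total | Plan |
|---|---|---|---|---|---|---|
| 25% vs 17.5% | 0.9516 | 0.4848 | 0.075 | 366.8 → 367 | 734 | 734 |
| 35% vs 24.5% | 1.0634 | 0.5405 | 0.105 | 233.3 → 234 | 468 | 468 |
| 18% vs 12.6% | 0.8374 | 0.4273 | 0.054 | 548.5 → 549 | **1098** | 968 |
| 20% vs 14% | 0.8738 | 0.4457 | 0.060 | 483.6 → 484 | **968** | – |

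Two exact matches identify the method. At the stated 18% the total is 1098, and 968 is 130 patients (11.8%) short of it. A 20% control rate returns 968 exactly.

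**Step 2: could another method give 968 at 18%?** One-sided variants give 1094 (unpooled variance), 1092 (arcsine), 1100 (null variance throughout) and 1170 (continuity-corrected). Two-sided versions give 1394, or 1468 with continuity correction. Reading the 30% decrease as an odds ratio of 0.7 gives 1490. None is within 3% of 968. Rounding of the rate does not explain it either: 19% gives 1030 and 19.5% gives 998.

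**Step 3: power at 18% vs 12.6%.** Power = Φ{[0.054 × √n − 0.8374] / 0.5077}, where n is per group and 0.5077 = √(p1(1 − p1) + p2(1 − p2)).

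- 968 evaluable (n = 484): Φ(0.691) = 75.5%
- 1066 enrolled, 10% lost (959.4 evaluable, n = 479.7): Φ(0.680) = 75.2%
- 1066 enrolled, none lost (n = 533): Φ(0.806) = 79.0%

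For 80% power at 18%, 1098 evaluable are needed, or 1098/0.9 = 1220 enrolled.

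**Step 4: attrition.** The plan multiplies: 968 × 1.1 = 1064.8, 734 × 1.2 = 880.8 and 468 × 1.2 = 561.6, rounded up to even totals of 1066, 882 and 562. To end with N after a loss fraction d, enrolment must be N/(1 − d).

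| Time | Needed | Enrolled (plan) | Left after loss | N/(1 − d), even arms | Power at plan's enrolment and loss |
|---|---|---|---|---|---|
| 30 days | 968 | 1066 | 959 | 1076 | 75.2% (at 18%) |
| 90 days | 734 | 882 | 706 | 918 | 78.6% |
| 180 days | 468 | 562 | 450 | 586 | 78.7% |

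At 30 days the attrition step accounts for only 75.5 − 75.2 = 0.3 points; the rest of the shortfall comes from the control rate. At 90 and 180 days it costs about 1.4 and 1.3 points.

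**The case against.** The strongest reply concerns consequence, not arithmetic. The plan predicts only a trend at 30 days and expects significance at 90 days and 6 months. The aims use 45, 90 and 180 days, and the chi-square comparison named under Analyses is at 6 months. If 1066 are enrolled and 20% are lost (about 853 evaluable), one-sided power is 85.0% at 90 days and 95.7% at 180 days, so the later comparisons are well covered at the headline size. All of this stands. It limits the damage, but it does not make the 80% claim at 30 days correct, and that claim is what generates 1066.

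A second reply is that the attrition step does what the text describes, and that its effect is small. Record review, telephone, mail and a death index should also recover some outcomes among patients who drop out. That is fair, although the records cover only the system's own hospitals. The point is secondary. It still bears on 562, which is the declared minimum sample: at the plan's own loss rate, stopping there falls slightly short of 80%.

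A third reply is that the documents do not show which rate was entered. This also stands: 18% with a relative decrease near 32% would give about 968 too. The text states 30%, however, and the exact match at 20%, together with the historical rate given in the same sentence, makes 20% much the likelier source.

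**Conclusion.** The concern holds. Under the plan's stated assumptions (18% control rate, 30% relative decrease, one-sided 0.05, equal arms), 80% power at 30 days needs 1098 evaluable patients, not 968. The stated 968 gives 75.5%, and 1066 enrolled with 10% lost gives 75.2%, a shortfall of about 5 points. That 968 came from a 20% control rate is a strong inference, not something the documents show.

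The base figures for 90 and 180 days are correct. The attrition slip is minor: it takes those time points to about 79% if enrolment stops at 882 or 562, assuming that every lost patient has no outcome. The finding does not imply that the 6-month comparison is underpowered at 1066.

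**What to change.** Correct the Sample Size paragraph, and carry the change into the opening summary and Sample and Setting. For the 30-day figure, choose one:

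- state that 968 is based on a reduction from 20% to 14%; or
- keep 18% and state that 1066 enrolled with 10% loss gives about 75% one-sided power at 30 days.

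For attrition, either compute enrolment as N/(1 − loss), which gives 1076, 918 and 586 from the plan's own base figures, or keep 882 and 562 and state power of about 79% at 90 and 180 days. If 1066 remains the target, it would help to add that power at 20% loss is then 85.0% at 90 days and 95.7% at 180 days.

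The cost is protocol wording and a slightly less favourable stated power. If power is restated, no extra patients are needed. Holding 80% at 18% would instead take 1220 enrolled, 154 more than planned.

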3. 45-day quality of life, functional status and perceived adherence to activity/exercise recommendations,
4. 7-day follow-up appointment with the healthcare provider assigned before discharge.

Specific aims and hypotheses:

1. Determine the effects of MyROAD on *first occurrence* and *time to first occurrence* of all-cause and HF hospitalization, ED visit, and death (or cardiac transplantation or VAD).

Hypothesis 1a: 45-day post-discharge rehospitalization, ED visit and death will be lower or trend toward lower, and 90- and 180-day first occurrence of hospitalization, ED visit and death will be lower in the MyROAD group compared to the usual care group.

Hypothesis 1b: Time to first event (rehospitalization, ED visit and death) will be longer in the MyROAD group compared to the usual care group at 90- and 180 days.

2. Determine the effects of receiving repetitive HF messages via MyROAD on quality of life, functional status and perceived adherence to activity recommendations.

Hypothesis 2a: Health-related quality of life (specifically, the clinical summary score, quality of life score, total symptom score -and subscales of physical limitations, symptom stability, symptom frequency, and symptom burden- will be higher in the intervention group compared to the usual care group at 45-days, reflecting improved early post-discharge quality of life. [Note: overall summary score (that includes the areas above and also self-efficacy) will be measured but are not included in the endpoint.]

Hypothesis 2b: HF-related symptoms will be less prevalent in number in the MyROAD group compared to the usual care group at 45-days.

Hypothesis 2c: Functional status will be higher in the intervention group compared with the usual care group at 45-days.

Hypothesis 2d: Perceived highest activity/exercise level will be higher in the intervention group compared with the usual care group at 45-days.

3. Determine the effects of receiving repetitive HF messages by MyROAD on adherence to 7-day follow-up appointment after index discharge.

Hypothesis 3: Adherence to 7-day follow up appointment will be higher in the intervention group compared with the usual care group.

METHODS

Design: The study will use a 2-group, randomized, placebo-controlled, single blinded, design. Healthcare providers will be initially blinded to group assignment, but may learn about the card from patient verbalization over time, as it is not possible to blind patients to the intervention, a MyRoad card.

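### The 1066 enrolment is sized on 30-day rehospitalization, which is not a listed outcome, and has 75.5% power, not 80%, at the stated 18% rate; the 6-month composite has no power statement

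*Combined protocol and SAP*

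**What the plan says.** The Sample Size section gives control rehospitalization rates for three time points. For the first, "a 30-day readmission rate of 18% is expected", after a historical rate of about 20% that is said to be falling slightly each year. The other two are 25% at 90 days and 35% at 180 days. The effect is a 30% decrease at each time, tested by one-sided Pearson chi-square at 0.05 with equal allocation. The result is: "A total sample size of 968, 734 and 468 are needed to achieve 80% power in 30-day, 90-day and 180-day rehospitalization rates".

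For attrition, "sample size was increased by 10-% at 30-days and 20% at 90- and 180-days". The 30-day size then becomes 1066 (533 in each arm), the 90-day size 882 and the 180-day size 562. The minimum is 562, with continuation to the 90-day size if trends are favorable. The abstract carries the 30-day figure as the trial's size: "A total of 1066 patients (968 + 10% attrition) with decompensated HF will be randomized". Sample and Setting also gives 1066.

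Study Purposes, Specific aims and hypotheses, and Outcomes and Measurement place the event outcomes at 45, 90 and 180 days. Hypothesis 1a asks only for a lower rate or a trend at 45 days, and predicts that "90- and 180-day first occurrence of hospitalization, ED visit and death will be lower in the MyROAD group". Sample Size says "we are hypothesizing that a trend will be seen at 30 days, but that there will be significant differences at 90 days and 6-months".

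Analyses names Pearson chi-square tests to "compare the proportion of subjects meeting the composite endpoint of death or at least 1 readmission by 6 months". It then calls Poisson regression of readmission rates and competing-risk time to first readmission secondary. The significance level is 0.05, with no sidedness stated there.

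**The concern.** Three links between sizing and analysis do not hold.

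- **Time point and rate.** The full enrolment rests on a 30-day proportion. That is not a listed outcome, and the plan expects only a trend there. The stated power also does not follow from the stated rate.
- **Endpoint.** Rehospitalization alone is powered, but the composite of death or readmission is tested. That composite appears to be primary only because the other analyses are called secondary. It has no assumed rate, no power and no sidedness.
- **Decision rule.** Differences are predicted at both 90 days and 6 months. Analyses gives no test for 45- or 90-day event proportions and no rule on which result carries the claim.

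A reader could not tell which comparison decides the trial, what power it had, or what error rate applies.

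**Working it through.** **Formula.** For control rate p1, card-group rate p2 = 0.7 × p1, p̄ = (p1 + p2)/2 and n per arm:

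n = [z_α √(2p̄(1−p̄)) + z_β √(p1(1−p1) + p2(1−p2))]² / (p1 − p2)²,

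with z_α = 1.645 (one-sided 0.05) and z_β = 0.842 (80% power). This is the pooled-variance chi-square formula.

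**Step 1: the plan's own figures.**

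| Time | p1 vs p2 | Total N for 80% | Plan |
|---|---|---|---|
| 180 days | 35% vs 24.5% | 468 | 468 |
| 90 days | 25% vs 17.5% | 734 | 734 |
| 30 days, stated rate | 18% vs 12.6% | 1098 | 968 |
| 30 days, historical rate | 20% vs 14% | 968 | 968 |

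Two exact matches confirm the formula. At 18%, other methods do not give 968 either: unpooled variance 1094, arcsine 1092, continuity correction 1170, two-sided 1394. The historical 20% appears to have been used in place of the stated 18%.

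**Step 2: power at 968 evaluable (484 per arm), one-sided.** It is 75.5% at 18% (exact enumeration 75.8%), 80.0% at 20% and 88.7% at 25%. If all 1066 were evaluable, power at 18% would be 79.0%.

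**Step 3: attrition.** 968 × 1.10 = 1065, which at 533 per arm is 1066, as stated. From the stated rate the same rule gives 1098 × 1.10 = 1208.

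**Step 4: power of the 6-month composite.** The plan gives no rate of death without readmission. I assume d = 0 to 10% per arm, unchanged by the card, so p1 = 0.35 + d and p2 = 0.245 + d. Each range runs from d = 0 to d = 10%.

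| Enrolled | Evaluable | One-sided | Two-sided |
|---|---|---|---|
| 562 | 468 (562/1.2) | 80–75% | 70–64% |
| 562 | 450 (562 × 0.8) | 79–74% | 68–62% |
| 882 | 734 (the plan's 90-day evaluable size) | 93–90% | 88–83% |
| 1066 | 853 (1066 × 0.8) | 96–93% | 92–88% |
| 1066 | 888 (1066/1.2) | 96–94% | 93–89% |

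If the 30% reduction instead applies to the whole composite at 40–45%, one-sided power is 87–92% at 468 evaluable and 85–91% at 450.

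**Step 5: false-positive rate with two late time points.** A patient rehospitalized by 90 days also counts at 180 days. The two test statistics therefore have correlation √[0.25(1−p) / (0.75p)], where p is the 180-day rate.

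| 180-day rate p | Correlation | Both significant | Either significant |
|---|---|---|---|
| 35% (rehospitalization) | 0.787 | 2.4% | 7.6% |
| 40% (composite, d = 5%) | 0.707 | 2.0% | 8.0% |
| 45% (composite, d = 10%) | 0.638 | 1.7% | 8.3% |

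The last column is 0.05 + 0.05 minus the column before it. These figures assume one-sided 0.05 tests and a fixed sample size.

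**The case against.** The strongest reply is that little hangs on 30-day power. The plan expects only a trend there, and the sizes behind its predicted differences, 734 and 468, are right. First-event proportions are cumulative, so the 45-day rate cannot be below the 30-day rate. Linear interpolation between 18% at day 30 and 25% at day 90 gives 18 + 7 × 15/60 = 19.75% at day 45, and 79.5% power at 968. Near-complete record capture could bring 30-day power to 79.0%. This limits the consequence, but the plan makes no 45-day assumption, and 79.0% requires no attrition where the plan allows 10%.

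The composite is not shown to be underpowered. Its power is high at 882 and 1066 even with no effect on death. The low end at 562 rests on that assumption, although Hypothesis 1a predicts fewer deaths and the eligibility criteria exclude patients with conditions implying under a year's survival. That stands: the gap is one of specification.

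Sample Size does imply a one-sided chi-square test at 90 days, so what is missing is its place in Analyses; 45 days has no event-proportion test in either section. A three-step order also leaves ED visits and HF-specific events uncovered, and the 7.6% counts only two of the possible tests.

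**Conclusion.** The concern holds. The 80% power behind 1066 is wrong at the plan's stated 18%. It is 75.5% at 968 evaluable, 4.5 points lower, and 80% would need 130 more evaluable patients (1098 − 968). The figure also describes a time point that is not among the outcomes. This part needs no assumption beyond the plan's own inputs.

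The composite's power and sidedness are unstated. At 562 enrolled, the choice of one or two sides moves power by about 10 points. Whether there is a real shortfall at 562 depends on the death-only rate and on whether the card affects it; at 1066 power is adequate on either reading. That the composite is primary is an inference, since the plan labels no primary endpoint.

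With no decision rule, the one-sided false-positive rate is 7.6–8.3% if either late time point suffices and 2.4–1.7% if both must succeed. These are corrections the plan should make. They do not show that the trial is too small.

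**What to change.** 1. **Sample Size and abstract.** Keep 1066 and correct its basis in one of two ways. Either list 30-day rehospitalization as an outcome, taken from dated medical-record events, and state 75.5% power at 18% (or say that 968 rests on 20%). Or size on 45 days with an assumed rate: one-sided power at 968 evaluable is 75.5–88.7% for rates of 18–25%, and reaches 80% if the rate is at least 20%.
2. **Analyses: primary endpoint.** Name the 180-day composite as primary and state its sidedness. Give its power at 562, 882 and 1066, using 20% attrition and a stated rate of death without readmission.
3. **Analyses: testing order.** Test the 180-day composite, then 90-day rehospitalization, then 45-day rehospitalization, each at full alpha, stopping at the first non-significant result. Alternatively, mark the 45-day result descriptive. Other orders are valid, but one must be fixed. Label ED-visit and HF-specific events as secondary or exploratory.

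**Cost.** Wording only, with no extra patients if 1066 is kept. Holding 80% at 45 days would take 1098 × 1.1 = 1208 enrolled at an 18% rate (142 more), or 734 × 1.1 = 808 at 25% (none extra). The fixed order costs no alpha at 180 days, but 90-day claims then also need 180-day success. Simulated one-sided 90-day power falls from about 80% to 77–79% at 734 evaluable, and from 85% to 82–85% at 853.

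This order assumes a fixed sample size. It does not control error across the extension beyond 562 on favorable trends, which needs its own rule.

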In brief, the research intervention is a novel card with 4 standardized, recorded messages of HF discharge instructions and a general message. (see Intervention section). The messages themselves are *not* the intervention, as the HF self-care messages are general standard of care messages delivered in many formats to hospitalized patients at all Cleveland Clinic hospitals. It is the ability to re-play (and re-listen) to general messages when desired that is the intervention.

Sample and Setting

A total of 1066 patients will be enrolled (533 per group) and consist of adults with chronic HF (diagnosis \geq 2 months) who are hospitalized for acute decompensated HF at the Cleveland Clinic main campus, Fairview Hospital, and Hillcrest Hospital. This sample size includes a 10% attrition rate.

Patients will have decompensated HF with preserved or reduced ejection fraction when hospitalized and New York Heart Association FC III or ambulatory IV. Diagnosis and etiology of HF will be confirmed in the electronic medical record prior to enrollment.

Inclusion Criteria:

1. Not referred for cardiac transplantation or ventricular assist device during the index hospitalization,
2. Minimum age 18 years (no upper age limit),
3. Ability to read and write,
4. Discharge to home or to a family member's home and has control of making self-care decisions,
5. Willing to participate; which requires three (3) follow-up telephone calls post-discharge.

Exclusions:

V1_01-20-16

NCT02901314

1. Chart documented psychiatric or cognitive conditions that limit ability to understand or adhere to self-care recommendations (Alzheimer's condition, dementia, schizophrenia, other neurological history that impairs memory),
2. Plans to discharge to assisted living apartment/center, skilled nursing facility or hospice care center,
3. Receiving home hospice or palliative care; or has a medical condition reflecting less than 1 year of survival (cachexia, end stage liver disease or cancer or non-ambulatory New York Heart Association functional class IV heart failure),
4. Post-cardiac transplantation or ventricular assist device placement,
5. Currently enrolled in another experimental HF research study,
7. Chronic renal failure and receiving chronic hemodialysis therapy for an estimated glomerular filtration rate $< 30 \text{ mL/minute/1.73 m}^2$,
8. A non-traditional form of HF (hypertrophic or restrictive forms of cardiomyopathy, congenital heart disease or Takotsubo cardiomyopathy).

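### Does sizing the trial on one-sided tests leave it underpowered, given that the Analyses section names no direction?

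*Combined protocol and SAP*

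**What the plan says.** Sample Size assumes control rehospitalization rates of 25% at 90 days and 35% at 180 days, a 30% decrease with the card and 80% power. It gives totals of 734 and 468 before attrition and states the test: "These calculations assumed a balanced randomization and use of one-sided Pearson chi-square tests with a significance level of 0.05". On attrition, "sample size was increased by 10-% at 30-days and 20% at 90- and 180-days", which gives 882 and 562. The smallest figure, 562, is called a minimum, with this rule: "If trends in outcomes are favorable, data collection will continue to reach the required sample size for 90-day outcomes". The abstract and Sample and Setting both give planned enrolment as 1066, or 533 per group.

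Analyses says "Pearson chi-square tests will be used to compare the proportion of subjects meeting the composite endpoint of death or at least 1 readmission", assessed by 6 months, and adds "Analyses will be performed assuming a 0.05 significance level". It does not say one-sided or two-sided, and it lists no chi-square test at 90 days.

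Hypothesis 1a is directional: 90- and 180-day events "will be lower in the MyROAD group compared to the usual care group". Sample Size predicts in the same vein that "there will be significant differences at 90 days and 6-months". Nothing in the document says two-sided.

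**The concern.** A Pearson chi-square statistic does not distinguish benefit from harm, so its usual p-value is two-sided. A statistician who read only the Analyses section could report that p-value at 0.05, while the trial was sized for a one-sided test at 0.05. The two readings part company when the card does better and the two-sided p lies between 0.05 and 0.10: the same data are then positive on one reading and negative on the other. The 80% power claim also depends on the reading. If direction could be settled after the results were seen, the error rate would not be controlled as planned.

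**Working it through.** **Inputs (Sample Size section).** Control rates p1 are 25% (90 days) and 35% (180 days). The 30% decrease is read as relative, since a 30-point drop from 25% is impossible, so p2 is 17.5% and 24.5%. Allocation is 1:1 and power is 80% (z = 0.842). The critical value is 1.645 one-sided or 1.960 two-sided.

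**Formulas (pooled variance, no continuity correction).** Write d = p1 − p2, p̄ = (p1 + p2)/2, A = √[2p̄(1 − p̄)] and B = √[p1(1 − p1) + p2(1 − p2)].

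- n per arm = (z_α·A + 0.842·B)² / d²
- power = Φ[(d√n − z_α·A)/B]

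**Reproducing the plan's totals**

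| | d | A | B | n per arm, one-sided | Total, one-sided | Total, two-sided |
|---|---|---|---|---|---|---|
| 90 days | 0.075 | 0.5785 | 0.5761 | 366.8, so 367 | 734 | 932 |
| 180 days | 0.105 | 0.6465 | 0.6422 | 233.3, so 234 | 468 | 594 |

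The one-sided totals match the document exactly.

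**Two-sided power at those totals**

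- 90 days, 367 per arm: (0.075·√367 − 1.960·0.5785)/0.5761 = 0.526, power 70.0%.
- 180 days, 234 per arm: (0.105·√234 − 1.960·0.6465)/0.6422 = 0.528, power 70.1%.

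**The test that Analyses lists (6 months), at each enrolment figure in the plan.** The 180-day rehospitalization rates are used. Loss runs from none to the 20% the plan allows for.

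| Enrolled | One-sided: no loss / 20% loss | Two-sided: no loss / 20% loss |
|---|---|---|
| 562 | 86.1% / 78.7% | 77.9% / 68.4% |
| 882 | 96.2% / 92.1% | 92.8% / 86.4% |
| 1066 | 98.3% / 95.7% | 96.4% / 92.0% |

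For 1066 with 20% loss, n = 0.8 × 533 = 426.4 per arm. Then (0.105·√426.4 − 1.960·0.6465)/0.6422 = 1.403, and power is 92.0%.

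**How often the two readings would disagree.** Under the planned effect this is one-sided power minus two-sided power. At 1066 it is 98.3 − 96.4 = 1.9 points with no loss and about 3.8 points with 20% loss. For example, with 426 per arm and 149 control events (35%), 123 to 126 card events fall in the disputed zone (two-sided p 0.056 to 0.092). With 122, z = 1.99 and p = 0.047, so both readings are positive.

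**Composite endpoint.** The listed test counts deaths as well, and the plan gives no rate for that. As an assumption, add 5 points of deaths to both arms, unaffected by the card: 40% versus 29.5%, A = 0.6734, B = 0.6693. Two-sided power at 1066 is then Φ[(0.105·√533 − 1.960·0.6734)/0.6693] = Φ(1.650) = 95% with no loss. With 20% loss it is Φ[(0.105·√426.4 − 1.960·0.6734)/0.6693] = Φ(1.267) = 90%. If instead the composite rate is 40% and the whole of it falls by 30%, to 28%, power is higher than for rehospitalization alone. The answer at 1066 does not turn on this choice.

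**The case for a change.** The strongest case for a change is that a sentence about what the calculations assumed is not a rule for the analysis, and that directional hypotheses can be tested either way. One added word would close the gap, and leaving it open permits a choice after the data are seen. Nor is 1066 guaranteed. At 562, two-sided power is 78% even with no loss. With 225 per arm (562 less 20%) and 79 control events, 60 to 62 card events would be significant one-sided only (two-sided p 0.053 to 0.084). At 90 days, where the plan also predicts significance, two-sided power is 78% to 68% at 882 and 85% to 76% at 1066.

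Part of this stands. Analyses is silent on direction, and the arithmetic is right. The consequence is weaker than it looks, for three reasons.

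- A result of 79 versus 60 to 62 events is a favourable trend, which the plan's own rule would most naturally carry on to 882. There two-sided power at 6 months is 86% to 93%. Stopping at 562 would mainly follow unfavourable trends, where neither reading is likely to give a positive result. Fixed-sample power at 562 therefore does not describe that stop. What counts as a favourable trend is a separate question.
- The 90-day figures concern a test that Analyses does not list. They apply only if the same chi-square is borrowed for Hypothesis 1a and run two-sided.
- Part of the shortfall at 562 and 882 with full loss comes from how attrition was added. Multiplying 468 by 1.2 gives 562, whereas dividing by 0.8 gives 585. That is a separate matter from direction.

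**Conclusion.** No change is called for. One-sided 0.05 is the only direction the document states. It appears in the section just before Analyses, for the same type of test at the same level, and it agrees with the directional hypotheses. Carried forward, it leaves the stated 80% at 734 and 468 intact. An analyst filling the gap from the plan would use it. An analyst who reported the more cautious two-sided p-value would still have about 92% to 96% power at 6 months with 1066 enrolled, and the two readings would differ in roughly 2% to 4% of trials under the planned effect. Replacing one-sided with two-sided would be a trade-off: it would let an excess of events with the card be declared significant, and it would lower the stated power.

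This rests on the plan's 35% control rate, a 30% relative reduction, loss of at most 20% and enrolment reaching 1066. The figures are for rehospitalization alone; the 5-point illustration for deaths gives 90% to 95%. If the trial ended at a smaller size, or a two-sided 90-day test were made decisive, power would be lower, as shown above. The plan does not commit to such a test.
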